16.3 Appendix 3: Specific Renal Alert Criteria and Actions and Event Follow-up

Table 16-4 Specific Renal Alert Criteria and Actions

Confirmed serum creatinine increase 25 – 49%	
 ● Consider causes and possible interventions ● Follow up within 2-5 days
Serum creatinine increase $\geq 50\%$ ⁺ OR if <18 years old, eGFR < 35 mL/min/1.73 m ²	
 ● Consider causes and possible interventions ● Repeat assessment within 24-48h if possible ● Consider drug interruption or discontinuation unless other causes are diagnosed and corrected ● Consider patient hospitalization and specialized treatment
New onset dipstick proteinuria $\geq 3+$ OR Protein-creatinine ratio (PCR) $\geq 1\text{g/g Cr}$ (or mg/mmol equivalent as converted by the measuring laboratory)	
 ● Consider causes and possible interventions ● Assess serum albumin & serum total protein ● Repeat assessment to confirm ● Consider drug interruption or discontinuation unless other causes are diagnosed and corrected
New onset hematuria $\geq 3+$ on urine dipstick	
Assess & document:
 
 ● Repeat assessment to confirm ● Distinguish hemoglobinuria from hematuria ● Urine sediment microscopy ● Assess sCr ● Exclude infection, trauma, bleeding from the distal urinary tract/bladder, menstruation ● Consider bleeding disorder

+ Corresponds to KDIGO criteria for Acute Kidney Injury

16.3.1 Renal Event Follow-Up

Table 16-5 Renal Event Follow-Up

Assess, document and record in CRF:
 
• Urine dipstick and sediment microscopy evidence of DIN: crystals, red blood cells (dysmorphic/glomerular vs. non-dysmorphic/non-glomerular), white blood cells, tubular epithelial cells• Blood pressure and body weight• Serum creatinine, BUN, electrolytes (sodium, potassium, phosphate, calcium), bicarbonate and uric acid• Urine output

Review and record possible contributing factors to the renal event (co-medications, other co-morbid conditions) and additional diagnostic procedures (MRI etc.) in the CRF

Monitor patient regularly (frequency at investigator's discretion) until -
 
• Event resolution: (sCr within 10% of baseline or PCR < 1 g/g Cr, or ACR <300 mg/g Cr) or• Event stabilization: sCr level with $\pm 10\%$ variability over last 6 months or proteincreatinine ratio stabilization at a new level with $\pm 50\%$ variability over last 6 months.• Analysis of urine markers in samples collected over the course of the DIN event

5.7	Rule of exclusion criteria of analysis sets.....	29
6	Reference	31

List of abbreviations

AE	Adverse Event
	Commercially Confidential Information
CRF	Case Report Form
CSR	Clinical Study Report
DMS	Document Management System
	Commercially Confidential Information
FAS	Full Analysis Set
	Commercially Confidential Information
IA	Interim Analyses
MedDRA	Medical Dictionary for Drug Regulatory Affairs
	Commercially Confidential Information
RAP	Reporting & Analysis Process
SAP	Statistical Analysis Plan
SAS	Statistical Analysis System
TFLs	Tables, Figures, Listings
WHO	World Health Organization

1 Introduction

Commercially Confidential Information

The Statistical Analysis Plan (SAP) describes the implementation of the statistical analysis planned in the protocol.

Final study protocol amendment (v02) is available at the time of finalization of Statistical Analysis Plan.

1.1 Study design

This is a multi-center, randomized, placebo-controlled, participant-and-investigator-blinded, sponsor open-label study in obese participants with or without T2DM. The study comprises a screening/baseline period of up to 35 days (5 weeks), a 14-week treatment period in which participants will be administered MBL949 or placebo at 8 biweekly intervals starting on Day 1 and a 10-week follow-up period.

Approximately 106 participants will be enrolled to ensure at least 90 participants complete week 16 to assess the primary objectives of safety, tolerability, and efficacy.

Commercially Confidential Information

Participants will be randomized to one of five MBL949 arms (shown below), or placebo, administered by subcutaneous (SC) injection every 2 weeks during treatment period (8 doses):

MBL949 Arm 1: Commercially Confidential Information

MBL949 Arm 2: Commercially Confidential Information

MBL949 Arm 3: Commercially Confidential Information

MBL949 Arm 4: Commercially Confidential Information

MBL949 Arm 5: Commercially Confidential Information

Commercially Confidential Information

Screening (Days -35 to -15)

Consented participants will undergo a screening visit between Day -35 and Day -15 to determine their eligibility for the study. Participants who meet eligibility criteria will be scheduled for baseline assessments.

Baseline (Days -14 to -1)

Prior to dosing (Day 1), participants who are eligible for enrollment following screening will return to the clinic to undergo baseline assessments. To facilitate study conduct, participants may come to the clinic on multiple days to complete the required assessments prior to Day 1,
Commercially Confidential Information

Randomization and Dosing (Day 1)

Commercially Confidential Information

Eligible participants, based on screening and baseline assessments, will be randomized into MBL949 arms 1-5 and placebo arm Commercially Confidential Information

On Day 1, participants will come to the clinic after an overnight fast of at least 10 hours to complete the Day 1 assessments prior to dosing.

Administration of MBL949 or placebo will be given via a SC injection according to instructions provided in the Pharmacy Manual. Dosing will be followed by an observation period of at least one hour post dose administration.

Treatment period (Days 1-99)

Following Day 1, the study treatment will be administered SC at biweekly intervals for a total of eight dose administrations over 14 weeks. Participants will be evaluated regularly throughout the treatment period for safety, tolerability, efficacy, CCI. Participants in consultation with the Investigator may select to have selected visits throughout the study to be conducted at home by a visiting nurse or at the study site.

Commercially Confidential Information

Follow Up (Days 100-169)

Participants will have a 10-week follow-up period (Day 100 to Day 169) CCI in which they will continue to be monitored for safety, tolerability, efficacy, Commercially Confidential Information

1.2 Study objectives, endpoints and estimands

Primary objective(s)

To evaluate the safety and tolerability of different dosing regimens of MBL949 in obese participants with or without T2DM	
Frequency and severity of adverse events (AEs)

To evaluate the effect of different dosing regimens of MBL949 on weight in obese participants with or without T2DM at week 16	
Weight

Exploratory objective(s)

Commercially Confidential Information

Commercially Confidential Information

Commercially Confidential Information

2 Statistical methods

2.1 Data analysis general information

Commercially Confidential Information

The final analysis will be conducted on all participant data at the time the trial ends. Details of these analyses are outlined in this document.

Data will be analyzed using SAS® version 9.4 (or higher).

Interim analyses

Commercially Confidential Information

Descriptive statistics

Descriptive statistics on continuous data will include mean, standard deviation, median, minimum, and maximum, while categorical data will be presented as frequencies and percentages.

In shift tables and tables of abnormal values all unscheduled assessments are included. Unscheduled assessments will be reported with the scheduled assessments in the listings.

2.1.1 General definitions

Study treatment refers to MBL949 or placebo. Commercially Confidential Information

The term '*date of first administration of study drug/treatment*' refers to the date on which the study drug/treatment was given for the first time in the CMBL949A12201 study.

The term '*date of last administration of study drug/treatment*' refers to the date on which the study drug/treatment was given for the last time in the CMBL949A12201 study.

The term '*study day*' refers to the Analysis Relative Day, Relative Start Day, or Relative End Day, as applicable. Day 1 is defined as the date of first dose of study drug (MBL949 or placebo).

Study day is defined as the number of days since the date of first dose of study treatment (Day 1).

Therefore, for a particular date, study day will be calculated as follows:

- for dates on or after the first administration of study treatment,
Study day = Assessment date – Date of first dose of study treatment +1
- for dates prior to the date of first administration of study treatment,
Study day = Assessment date – Date of first dose of study treatment.

The term '**baseline**' refers to the last non-missing assessment prior to the first dose of study drug, unless specified otherwise.

The term '**Treatment period**' refers to the 14 weeks period from Day 1 to Day 99.

The term '**treatment-emergent adverse event**' refers to any adverse event (AE) started after the first dose of study medication, or events present prior to the start of treatment but increased in severity based on preferred term (PT).

2.2 Analysis sets

For all analysis sets, participants will be analyzed according to the study treatment(s) received.

The **safety analysis set** will include all participants that received any study drug.

The **full analysis set (FAS)** will include all randomized participants.

Commercially Confidential Information

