Premature participant withdrawal	Point/time when the participant exits from the study prior to the planned completion of all study drug administration and/or assessments; at this time all study drug administration is discontinued and no further assessments are planned
Randomization number	A unique identifier assigned to each randomized participant
Screen Failure	A participant who did not meet one or more criteria that were required for participation in the study
Source Data/Document	Source data refers to the initial record, document, or primary location from where data comes. The data source can be a database, a dataset, a spreadsheet or even hard-coded data, such as paper or eSource
Start of the clinical trial	The start of the clinical trial is defined as the signature of the informed consent by the first participant
Study treatment	Any drug or combination of drugs or intervention administered to the study participants as part of the required study procedures; includes investigational drug(s), control(s) or background therapy
Study treatment discontinuation	When the participant permanently stops taking any of the study drug(s) prior to the defined study treatment completion date (if any) for any reason; may or may not also be the point/time of study discontinuation
Treatment arm/group	A treatment arm/group defines the dose and regimen or the combination, and may consist of 1 or more cohorts.
Treatment of interest	The treatment of interest and, as appropriate, the alternative treatment to which comparison will be made. These might be individual interventions, combinations of interventions administered concurrently, e.g. as add-on to standard of care, or might consist of an overall regimen involving a complex sequence of interventions. This is the treatment of interest used in describing the related clinical question of interest, which might or might not be the same as the study treatment.
Variable (or endpoint)	The variable (or endpoint) to be obtained for each participant that is required to address the clinical question. The specification of the variable might include whether the participant experiences an intercurrent event.

Withdrawal of study consent (WoC)	Withdrawal of consent from the study occurs only when a participant does not want to participate in the study any longer and does not allow any further collection of personal data

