
Key Inclusion criteria
	
ALL participants:
 
Participants must be between 18 to 60 years of age inclusive
 
 • At screening participants must have: • Body mass index (BMI) ≥ 32 kg/m², BMI = body weight (kg) / [Height (m)]² • Weight ≥ 77 kg, stable weight i.e., less than 1.5 kg self-reported change within 90 days and/or 3 kg self-reported weight loss within 6 months before screening 
Participants with T2DM
 
 • Diagnosed diabetes duration less than 10 years • Hemoglobin A1C below $\leq 9\%$ • C-peptide ≥ 0.2 ng/ml • If treated for T2DM, treatment may be limited to diet and exercise. In addition, treatment with one of the following anti-diabetic agents is permitted (stable for approximately 3 months prior to randomization): • Metformin • SGLT2 inhibitors (if prescribed as the first line i.e. single agent) • DPP4 inhibitors • Acarbose

Key Exclusion criteria
	
ALL participants:
 
Participants with:
 
 • Systolic blood pressure less than 95 mmHg or greater than 155 mm Hg • Diastolic blood pressure less than 60 mgHg or greater than 95 mg Hg • Pulse rate less than 56 bpm or greater than 110 bpm • History or presence of symptomatic cardiovascular disease such as angina pectoris, prior ASCVD events (including stroke, myocardial infarction, heart failure, claudication), or prior coronary revascularization 
Commercially Confidential Information

	
Commercially Confidential Information
 
 • Participation in an organized weight reduction program (e.g. Weight Watchers, NutriSystem) or any investigational weight loss trial within 6 months before screening 
Commercially Confidential Information

Study treatment	
 • MBL949 • Placebo
Treatment of interest	The randomized treatment (MBL949 or placebo)
Efficacy assessments	
 • Weight (kg)
	
Commercially Confidential Information

Key safety assessments	
 • Adverse Events • Serious Adverse Event
	
Commercially Confidential Information

Data analysis	The primary endpoint for efficacy is change in weight from baseline to week 16. Primary endpoints for safety and tolerability include frequency and severity of adverse events. Commercially Confidential Information

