6.4 Treatment blinding

This is a participant-and investigator-blinded, sponsor open-label study. Participants and investigators will remain blinded to study treatment throughout the study, except where indicated below.

The identity of the treatments will be concealed by the use of study drugs that are all identical in packaging, labeling, schedule of administration, appearance, and odor.

Site staff

With the exception of any unblinded site staff listed below, all site staff (including study investigator, study nurse, CCI) will be blinded to study treatment throughout the study.

- Designated unblinded site staff, CCI for dose administration: required due to the range of different dose levels and to maintain the investigator and site staff blinding.
- Unblinded pharmacist who is independent of the study team will be required in order to manage drug product supplied in bulk and prepare doses.

This unblinded pharmacist will receive a randomization assignments via IRT. Appropriate measures must be taken by the unblinded pharmacist to ensure that the treatment assignments are concealed from the rest of the site staff, with the exception of the designated unblinded site staff who will administer the dose.

Unblinding a single participant at site for safety reasons (necessary for participant management) will occur via the IRT system.

Sponsor staff

The following unblinded sponsor roles are required for this study:

- Unblinded field monitor(s)
- Unblinded clinical staff managing drug re-supply to site
- Commercially Confidential Information

The unblinded field monitors are required to review drug accountability and allocation at site. The unblinded monitors are not provided with a randomization list directly but will be unblinded through review of source documentation compiled by the unblinded pharmacist, which details treatment allocation to individual participants. The unblinded monitors will also be able to review the treatment allocation cards/randomization list provided to the unblinded pharmacist. The names of the unblinded monitor(s) are detailed in the monitoring plan.

Sponsor clinical staff are required to assist in the management and re-supply of investigational drug product. These individuals are not provided with randomization lists directly, but may be unblinded through communication of drug re-supply needs via the unblinded site pharmacists.

Commercially Confidential Information

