10.1.5 Reporting of study treatment errors including misuse/abuse

Medication errors are unintentional errors in the prescribing, dispensing, administration or monitoring of a medicine while under the control of a healthcare professional, participant or consumer (EMA definition).

Misuse refers to situations where the medicinal product is intentionally and inappropriately used not in accordance with the protocol.

Abuse corresponds to the persistent or sporadic, intentional excessive use of a medicinal product, which is accompanied by harmful physical or psychological effects.

Study treatment errors and uses outside of what is foreseen in the protocol will be recorded on the appropriate CRF irrespective of whether or not associated with an AE/SAE and reported to Safety only if associated with an SAE. Misuse or abuse will be collected and reported in the safety database irrespective of it being associated with an AE/SAE within 24 hours of Investigator's awareness.

Table 10-1 Guidance for capturing the study treatment errors including misuse/abuse

Treatment error type	Document in Dosing CRF (Yes/No)	Document in AE eCRF	Complete SAE form
Unintentional study treatment error	Yes	Only if associated with an AE	Only if associated with an SAE
Misuse/Abuse	Yes	Yes	Yes, even if not associated with a SAE

For more information on AE and SAE definition and reporting requirements, please see the respective sections.

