12.4.8 Supportive analyses

To evaluate the effect of intercurrent events on efficacy/safety results, primary analysis may be performed on FAS including/excluding some intercurrent events cases described in [Section 12.4.4](#) as seen fit.

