3.1 Primary endpoint(s)

Commercially Confidential Information

At final analysis, MBL949 arms 1, 2, and 3 (if not terminated early) will each have 12 participants, and the placebo arm will have at least 24 participants who complete week 16 weight assessment. Therefore, MBL949 efficacy group will have a sample size of either 24 or 36. Conservatively assuming that the efficacy group and placebo arm each has 24 participants, the power for efficacy criteria is still 95%.

At final analysis, if MBL949 arm 4 has been triggered and completed, the weight change of this arm will be compared to MBL949 efficacy group.

Commercially Confidential Information

Weight change in MBL949 arm 4 will be compared against placebo arm and MBL949 efficacy group, respectively. Assuming that the true weight change in MBL949 arm 4 is -2kg, there is at least 77% probability of declaring MBL949 arm 4 having more weight loss than placebo, and at least a 99% probability of declaring MBL949 efficacy group having more weight loss than MBL949 arm 4, given sample sizes of 12, ≥ 24 , and ≥ 24 in MBL949 arm 4, MBL949 efficacy group, and placebo arm, respectively, where type I error rate is 0.1.

Commercially Confidential Information

4 Change to protocol specified analyses

No change from protocol specified analysis was made.

5 Appendix

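### The analysis-set rule groups even the full analysis set by treatment received: this does not align with the protocol's randomised treatment of interest and leaves never-dosed participants without a group

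*SAP*

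**What the plan says.** Protocol 12.1 and SAP 2.2 carry the same sentence: "For all analysis sets, participants will be analyzed according to the study treatment(s) received". Both then define the safety set as participants given any study drug, and both say that the FAS "will include all randomized participants". No visible text exempts the FAS or efficacy from the rule, and SAP section 4 declares no change from the protocol.

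The protocol summary gives the treatment of interest as "The randomized treatment (MBL949 or placebo"). The glossary says of that term: "This is the treatment of interest used in describing the related clinical question of interest". It goes on to allow the treatment of interest to differ from the study treatment.

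Protocol 8.1.2 expects that some participants may be randomised and never start treatment, and classes them as early terminators. Protocol 12.4.8 gives the only visible link between the FAS and the weight analysis, a supportive run: "primary analysis may be performed on FAS including/excluding some intercurrent events cases".

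**The concern.** Randomisation makes the groups comparable as they were allocated. If participants are moved to the treatment they received, that comparability depends on the reason for the mismatch being unrelated to expected weight change. In the mixed model for repeated measures (MMRM), a regrouped participant would normally take every visit to the new group, so earlier weights give no protection. With 12 completers per arm, one participant can be seen in the estimate.

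There is also a gap in definition. A participant who is randomised but never dosed is in the FAS and has received nothing, so the rule assigns no group. Nor does the visible text say what received means for someone given more than one treatment.

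The rule should be settled before anyone knows whether a mismatch has occurred. That matters more here because protocol 6.4 lets the study statistician see the randomisation list at any time.

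**Working it through.** **1. The passages side by side.** The FAS is defined by randomisation and the treatment of interest is the randomised one, but the grouping in every set is by treatment received. The glossary clause allowing a different treatment of interest does not resolve this, because the summary then names the randomised treatment.

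**2. The plan's own number.** Completers: 5 × 12 on MBL949 plus 12 + 12 + 6 on placebo = 90. With 15% dropout, 90 / 0.85 = 105.9, so 106 as stated. The grouping rule does not change it.

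**3. SD (assumed, because it is redacted).** SAP 3.1 gives at least 77% probability for arm 4 (12 participants, true change -2 kg) against placebo (at least 24) at type I error 0.1. The placebo change and sidedness are not visible. Solving the two-sample t-test power for SD at exactly 77%, 12 v 24:

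| Assumed placebo change | SD, one-sided 0.1 | SD, two-sided 0.1 |
|---|---|---|
| 0 kg | 2.77 kg | 2.33 kg |
| -0.5 kg | 2.07 kg | 1.74 kg |
| -1 kg | 1.38 kg | 1.16 kg |

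As the stated power is a minimum, these are upper values under each assumption.

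**4. Shift from one regrouped participant.** Suppose one of n participants randomised to MBL949 receives placebo throughout and is counted with m placebo participants. Let d be how much less weight, in SD, that participant would lose than the arm average. Removing the participant moves the arm mean by d × SD / (n - 1), and adding the participant moves the placebo mean by d × SD / (m + 1). So

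shift = d × SD × (1/(n - 1) + 1/(m + 1)).

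- 12 v 24: 1/11 + 1/25 = 0.131
- 24 v 24: 1/23 + 1/25 = 0.083
- 36 v 24: 1/35 + 1/25 = 0.069

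The last two rows apply because SAP 3.1 says "MBL949 efficacy group will have a sample size of either 24 or 36". Swaps among the arms in that group leave its pooled comparison unchanged. For 12 v 24 and |d| = 1, the shift is 0.131 × 1.16 = 0.15 kg up to 0.131 × 2.77 = 0.36 kg. For |d| = 0.5 it is 0.08 to 0.18 kg. Positive d favours the drug and negative d favours placebo.

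**5. Type I error.** Simulation under no drug effect, 12 v 24, 400,000 runs. The misdosed participant's mean is d SD and the other arm members' mean is -d/11 SD, so the arm as a whole averages zero.

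| d | As received, one-sided 0.1 | As received, two-sided 0.1 |
|---|---|---|
| -1 | 0.049 | 0.116 |
| -0.5 | 0.072 | 0.103 |
| 0 | 0.100 | 0.100 |
| 0.5 | 0.134 | 0.104 |
| 1 | 0.174 | 0.116 |

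Grouped as randomised, the one-sided error stays at 0.096 to 0.101. If the sign is unknown, the as-received one-sided error averages (0.134 + 0.072)/2 = 0.103 at |d| = 0.5 and (0.174 + 0.049)/2 = 0.11 at |d| = 1. For the pooled groups at d = 1 it is 0.156 (24 v 24) and 0.151 (36 v 24).

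**6. What as-randomised grouping costs.** One fully misdosed participant in arm 4 dilutes the effect by 1/12. With placebo change 0, this takes it from 2 kg to 2 × 11/12 = 1.83 kg. Power falls from 0.77 to 0.716 (one-sided) or 0.705 (two-sided). Grouped as received, power is 0.756 or 0.753.

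**The case against.** The strongest reply has four parts.

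- **The summary line is only an estimand attribute.** It names the interventions to be compared and does not state a grouping rule. This is fair, and it is why the passages are called not aligned rather than flatly contradictory. It does not remove the as-received sentence, which covers every set.
- **Nothing visible ties the rule to the primary weight analysis.** A reader might infer that the primary estimand is as-treated. The documents do not support that: the efficacy set, the intercurrent-event handling and most of the weight method are redacted, and the run on the FAS in protocol 12.4.8 is optional and supportive.
- **Prognosis-related misdosing is not predicted.** A reader might infer it from protocol 10.1.5 ("Study treatment errors and uses outside of what is foreseen in the protocol will be recorded on the appropriate CRF") and from the words "required due to the range of different dose levels" in protocol 6.4. The first is general error-reporting text. The second explains why unblinded staff give the doses. The plan also has assignment by interactive response technology, an unblinded pharmacist, monitor review of allocation, and a ban on dose modification in protocol 6.5. No error rate or link to prognosis is given.
- **The numerical case is extreme.** It needs the wrong treatment at all eight doses and a prognosis well away from the arm average. Quoting only the 0.17 end would be one-sided, since the opposite sign gives 0.05. As-randomised grouping also costs some power.

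All four limit the size of the point. None supplies a reason to group an FAS of all randomised participants by treatment received, or says where never-dosed participants go.

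**Conclusion.** The point holds as a defect in the stated rule. Protocol 12.1 and SAP 2.2 give up randomised grouping for the FAS and for any efficacy analysis they govern, out of line with the protocol's treatment of interest, and they leave randomised, never-dosed participants without a group.

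The effect is nil if everyone receives the assigned treatment. If a mismatch is unrelated to prognosis, type I error stays at 0.10. With one fully misdosed participant in a 12-person arm, the contrast with 24 placebo participants shifts by about 0.13 × d × SD in either direction. For d from -1 to 1, one-sided error is about 0.05 to 0.17 and two-sided about 0.10 to 0.12. The kilogram figures rest on an SD back-solved from the 77% power under an assumed placebo change of 0 to -1 kg.

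The never-dosed gap is firm in the text but probably has little effect on the weight results. Such participants would often lack the post-baseline weight that protocol 12.4.5 and SAP 2.5.4 require. It matters for summaries by treatment group on the FAS, such as concomitant medication in protocol 12.3, which SAP 2.4 places on the safety set instead.

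Expected impact is low. It remains worth correcting because the correction is cheap. The documents do not show that the primary analysis is biased or that its error rate is inflated.

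**What to change.** In protocol 12.1 and SAP 2.2, replace the single grouping sentence with three statements:

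1. The FAS and all efficacy analyses are grouped by randomised treatment, including participants who were never dosed.
2. The safety set is grouped by treatment received.
3. For anyone given more than one treatment, received is defined by a rule fixed in advance, for example the treatment given at most of the administered doses.

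Cost: a SAP revision and a written protocol amendment with the approvals in protocol 14.1. No new data are needed and the planned 106 is unchanged. The statistical cost arises only if misdosing occurs: for one fully misdosed arm 4 participant, power is about 0.71 as randomised against about 0.75 as received.

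Two neighbouring matters are separate and minor, and should be raised on their own: the permissive wording on excluding COVID-impacted observations in SAP 5.5, and the use of the safety set for screened and randomised counts in SAP 2.3.1.
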